### 3. ELIGIBILITY CRITERIA

#### 3.1 Inclusion Criteria

Subject must meet all of the following applicable inclusion criteria to participate in this study:

1. Age  $\geq$  18 years.
2. Measurable disease according to RECIST 1.1 within 28 days prior to registration.
3. Documented pathologic diagnosis of RCC. All subtypes eligible including but not limited to clear cell, papillary, chromophobe, collecting duct carcinoma, medullary carcinoma, and unclassified categories. Sarcomatoid and rhabdoid differentiation are allowed.
4. Patients with clear cell histology must have demonstrated: 1) Progression on at least one prior anti-angiogenic agent unless intolerable; AND 2) progression on at least one agent that blocks the PD-1 pathway unless felt by the treating physician to be contraindicated (examples include but are not limited to: patients with autoimmune disease or patients requiring systemic steroids greater than 10 mg/day prednisone or its equivalent) or if they have been discontinued due to toxicity. Prior rapalogues are allowed.
5. Patients with non-clear cell histology must have received at least one prior anti-cancer therapy. Prior rapalogues are allowed.
6. Eastern Cooperative Oncology Group (ECOG) performance status of 0-2 (Appendix A).
7. Left ventricular ejection fraction (LVEF) greater than or equal to the lower limit of normal (LLN) as assessed by either multigated acquisition (MUGA) scan or echocardiogram (ECHO).
8. Must have adequate organ and bone marrow function.

System	Laboratory Value
Hematological	
Absolute Neutrophil Count (ANC)	$\geq$ 1500 cells/ $\mu$ L (without use of G-CSF 4 weeks prior to enrollment)
Hemoglobin (Hgb)	$\geq$ 9 g/dL (transfusions allowed)
Platelets (Plts)	$\geq$ 100 k/mm 
Renal	
Calculated creatinine clearance Cockcroft-Gault formula will be used to calculate creatinine clearance	$\geq$ 30 mL/min
Urinalysis	For patients with 2+ proteinuria on urinalysis, 24 hour urine collection should be obtained. 24 hour urine protein should be < 2 grams.
Hepatic	

Bilirubin	$\leq 1.5 \times$ upper limit of normal (ULN). For subjects with Gilbert's disease $\leq 3.0$ mg/dL
Aspartate aminotransferase (AST)	$\leq 2.5 \times$ ULN; $\leq 5 \times$ ULN if liver metastases are present
Alanine aminotransferase (ALT)	$\leq 2.5 \times$ ULN; $\leq 5 \times$ ULN if liver metastases are present
Metabolic	
Glycosylated hemoglobin (HbA1c)	$< 7.0\%$ ,
Fasting serum glucose	$\leq 130$ mg/dL
Fasting triglycerides	$\leq 300$ mg/dL

9. Recovery to baseline or  $\leq$  grade 1 Common Terminology Criteria for Adverse Events (CTCAE) version 4.0 from toxicities related to any prior treatment, unless adverse events are clinically non-significant and/or stable on supportive therapy.
10. Capable of understanding and complying with the protocol requirements and has signed the informed consent document. Voluntary written consent must be given before performance of any study related procedure not part of standard medical care, with the understanding that consent may be withdrawn by the subject at any time without prejudice to future medical care.
11. Submission of formalin-fixed, paraffin-embedded (FFPE) archival tumor specimens from the previous 18 months, if available. If not available, a fresh tumor biopsy prior to treatment initiation is MANDATORY unless determined medically unsafe or not feasible by the site investigator.
  - The archival specimen must contain adequate viable tumor tissue.
  - Specimens may consist of a tissue block (preferred and should contain the highest grade of tumor) or a recommended minimum of 20 unstained serial sections. Fine-needle aspiration, brushings, cell pellet from pleural effusion, bone marrow aspirate/biopsy are not acceptable.
  - Distant metastases specimens are preferred but if not available primary nephrectomy specimens are acceptable.
12. Subjects who experience a disease response per RECIST 1.1 criteria followed by subsequent progression will be required to have a post-treatment biopsy if feasible and safe.
13. Sexually active subjects and their partners must agree to use medically accepted methods of contraception.
  - For women:
    - Postmenopausal for at least 1 year before the screening visit, OR
    - Surgically sterile, OR
    - Agree to practice 1 effective method of contraception and 1 additional effective (barrier) method at the same time, from the time of signing the informed consent through 90 days (or longer, as mandated by local labeling [eg. USPI, SmPC, etc.] after the last dose of study drug, OR
    - Agree to practice true abstinence, when this is in line with the preferred and usual lifestyle of the subject (Periodic abstinence [e.g. calendar, ovulation, symptothermal, postovulation methods] and withdrawal, spermicides only, and lactational amenorrhea are not acceptable methods of contraception. Female and male condoms should not be used together.)

- For men:
  - Even if surgically sterilized (ie, status post-vasectomy), they must agree to practice highly effective barrier contraception during the entire study treatment period and through 120 days after the last dose of study drug, OR
  - Agree to practice true abstinence, when this is in line with the preferred and usual lifestyle of the subject (Periodic abstinence [e.g, calendar, ovulation, symptothermal, postovulation methods for the female partner] and withdrawal, spermicides only, and lactational amenorrhea are not acceptable methods of contraception. Female and male condoms should not be used together.)
  - Agree not to donate sperm during the course of this study or 120 days after receiving their last dose of study drug.

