### 3.2 Exclusion criteria

1. Subjects with a history of deep vein thrombosis (DVT) or pulmonary embolism (PE) within 6 months of study treatment initiation.
2. Receipt of any type of small molecular kinase inhibitor (including investigational kinase inhibitors) within 2 weeks of enrollment or receipt of any anti-cancer therapy (including investigational therapy, monoclonal antibodies, cytokine therapy) within 3 weeks of enrollment.
3. Treatment with any investigational products within 3 weeks before the first dose of study drug.
4. Radiation therapy for bone metastases within 2 weeks, other external radiation therapy within 4 weeks of enrollment.
5. Received prior hemibody external radiotherapy.
6. Known brain metastases or cranial epidural disease unless adequately treated with radiotherapy, radiosurgery, or surgery and stable for at least 4 weeks prior to enrollment as documented by magnetic resonance imaging (MRI) or computed tomography (CT) imaging. Treated brain metastases are defined as having no ongoing requirement for steroids and no evidence of progression or hemorrhage after treatment for at least 4 weeks prior to enrollment as documented by MRI or CT imaging.
7. Imminent or established spinal cord compression based on clinical and/or imaging. In subjects with untreated imminent or established spinal cord compression, treatment with standard of care as clinically indicated should be completed at least 4 weeks before enrollment.
8. The subject has a history of any of the following within the last 6 months before administration of the first dose of the drug:
  - Ischemic myocardial event, including angina requiring therapy and artery revascularization procedures
  - Ischemic cerebrovascular event, including transient ischemic attack and artery revascularization procedures

- Requirement for inotropic support (excluding digoxin) or serious (uncontrolled) cardiac arrhythmia (including atrial flutter/fibrillation, ventricular fibrillation or ventricular tachycardia)
  - Placement of a pacemaker for control of rhythm
  - New York Heart Association (NYHA) Class III or IV heart failure
  - Significant active cardiovascular or pulmonary disease including:
    - Uncontrolled hypertension defined as sustained BP >160 mm Hg systolic or > 95 mm Hg diastolic despite optimal antihypertensive treatment.
    - Pulmonary hypertension
    - Uncontrolled asthma or O2 saturation < 90% by arterial blood gas analysis or pulse oximetry on room air

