### **5.4.1 Allowed Concomitant Medications**

- Histamine H2 receptor antagonists may be allowed, if needed provided that the histamine H2 receptor antagonist is not taken within 12 hours before and within 6 hours after study drug administration. Subjects receiving histamine H2 receptor antagonists before enrollment must stop using these medications for at least 24 hours before their first dose of study drug. Examples of histamine H2 receptor antagonists include ranitidine, famotidine, and nizatidine. Cimetidine, a moderate cytochrome P450 (CYP)1A2 inhibitor, is not recommended as a first choice H2 receptor antagonist.
- Low molecular weight heparin (LMWH) is allowed
- Palliative XRT to pre-existing lesion is allowed
- Other medications considered necessary for the subject's safety and well-being may be given at the discretion of the site investigator. Any concomitant medications added or discontinued during the study should be recorded on the Case Report Forms (CRF).
- Neutralizing antacid preparations (acid neutralizers) and calcium supplements are not permitted during Cycle 1 on study drug administration days, but may be taken as needed on non-TAK-228 administration days. However, for all other cycles of the study administration of neutralizing antacids and calcium preparations is permitted except from 4 hours before until 2 hours after TAK-228 administration. Some anti-gas preparations may also have antacid properties, and should also not be permitted from 4 hours before until 2 hours after study drug administration

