### **5.4.2 Prohibited Concomitant Medications**

The following medications/therapies are prohibited during the study:

- Other investigational agents or mTOR inhibitors.
- Other anticancer therapies including chemotherapy, immunotherapy, radioimmunotherapy, targeted agents, radiation or surgery (subjects can have palliative radiation or surgery in the study for pre-existing lesions).

- Systemic corticosteroids (either IV or oral steroids, excluding inhalers or intraarticular, intraocular steroids) unless necessary for treatment of TAK-228 related AE (such as, rash).
- Anti-epileptic drugs for subjects with treated brain metastasis.
- Concomitant administration of any PPI is not permitted during the study. Subjects receiving PPI therapy before enrollment must stop using the PPI for 7 days before their first dose of study drugs. Examples of PPIs include omeprazole, esomeprazole, pantoprazole, lansoprazole, and rabeprazole.
- Strong CYP1A2 inhibitors and CYP inducers should be administered with caution, at the discretion of the investigator (see Appendix C). Alternative treatments, if available, should be considered.
- Use of concomitant medications that are known to prolong the QTc interval is strongly discouraged. If use is medically indicated, caution is advised with increased EKG for QTc monitoring.

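### Criterion 4 waives prior PD-1 therapy for clear-cell patients who need systemic steroids, but Section 5.4.2 prohibits those steroids on study with no provision for a need present at entry

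*Combined protocol and SAP*

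**What the plan says.** **At entry.** Under criterion 4 of Section 3.1, clear-cell patients must have shown "progression on at least one agent that blocks the PD-1 pathway unless felt by the treating physician to be contraindicated", or have stopped such an agent for toxicity. The criterion illustrates contraindication with two non-exhaustive examples: autoimmune disease, and "patients requiring systemic steroids greater than 10 mg/day prednisone or its equivalent".

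**On study.** Section 5.4.2 opens with "The following medications/therapies are prohibited during the study". Its list includes "Systemic corticosteroids (either IV or oral steroids, excluding inhalers or intraarticular, intraocular steroids) unless necessary for treatment of TAK-228 related AE". The entry sets no dose threshold.

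**Elsewhere.** Section 3.2 has no general bar on steroid use. Exclusion 6 mentions steroids only for brain metastases: "Treated brain metastases are defined as having no ongoing requirement for steroids and no evidence of progression or hemorrhage after treatment". Exclusion 9 mentions corticosteroids permissively, allowing enrolment after past transient glucose intolerance that they caused. Section 5.4.1 adds a general clause: "Other medications considered necessary for the subject's safety and well-being may be given at the discretion of the site investigator".

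**The concern.** The waiver in criterion 4 is written for, among others, patients with a current need for systemic steroids. The on-study rule then forbids that drug class except for an adverse event caused by the study drug. A patient who needs steroids for some other reason before the first dose fits the waiver and does not fit the exception.

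Three things are at stake.

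- **Patient care.** Read literally, the prohibition would mean withdrawing a drug that the patient is described as requiring, with no taper or timing stated.
- **Compliance.** Appendix E (3.7.3) permits no eligibility exception without IRB approval, and 3.8.2 classes any departure without prospective approval as a violation. Section 5.5 does not name use of a prohibited medication as a reason to stop protocol therapy, so the consequence of a breach is not spelled out.
- **Analysis set.** The evaluable population in Section 12.4 does not remove such a patient, who would therefore count in the primary response rate.

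**Working it through.** The plan gives no figure on this point and no formula applies. The check sets the provisions side by side and asks whether one patient can satisfy all of them.

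**The patient.** Clear-cell histology; progressed on an anti-angiogenic agent; no prior PD-1 agent because of a systemic steroid need above the dose in criterion 4; that need continues at Cycle 1 Day 1; no brain metastases; every other criterion met.

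| Provision | Effect on this patient |
|---|---|
| 3.1, criterion 4 | PD-1 requirement waived; the patient matches a named example |
| 3.1, criterion 10 | General ability to comply with the protocol; steroids not mentioned |
| 3.2, exclusion 6 | Not applicable (brain metastases only) |
| 3.2, exclusion 9 | Permissive on past steroid-induced glucose intolerance; does not exclude |
| 5.4.2, steroid entry | Oral and IV systemic steroids prohibited |
| 5.4.2, exempt forms | Inhaled, intraarticular and intraocular only; not met |
| 5.4.2, adverse event exception | Needs a TAK-228 related event; not met before the first dose |
| 5.4.1, discretion clause | Covers other medications; does not say that it overrides a named prohibition |
| 6.3, toxicity tables | Steroids as treatment for on-study events (pneumonitis, mucositis, rash); not baseline use |

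**Step 1: does entry screening remove the patient?** No exclusion criterion does so.

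**Step 2: does an on-study exception cover the patient?** The exceptions are the non-systemic forms and treatment of a TAK-228 related event. Neither reaches a need that existed before treatment.

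**Step 3: does a transition rule bridge the two?** None is given for steroids. For proton pump inhibitors, by contrast, exclusion 20 bars use at entry, and Section 5.4.2 bars use on study and states a 7-day stop before the first dose. The protocol pairs entry and on-study rules where it intends both; for steroids the pair is missing and criterion 4 points the other way.

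**Result.** For this patient the provisions cannot all be met. If the steroid need had ended before Cycle 1 Day 1, they could be.

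**Effect on the design.** Section 12.3 rests on response rates of 5% and 20%, 38 evaluable subjects from 40 enrolled, and the stage boundaries. None of these depends on the steroid rule, so type I error and power do not change.

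**The case against.** The best case for leaving the text alone is that criterion 4 is a prior-therapy criterion. It waives one requirement, authorises no steroid on study, and leaves all other criteria in force. Read together with criterion 10 and Section 5.4.2, a patient who cannot stop steroids could simply be treated as unsuitable. That reading is available, but it is only implicit, and it turns away the kind of patient whom the example describes. It shows how a site might resolve the conflict, not that the protocol has resolved it.

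The discretion clause in Section 5.4.1 could be offered as the answer from the other side. It is general, while the steroid prohibition is specific; if it overrode named prohibitions, they would have no force.

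Several stronger readings are tempting, and the documents do not support them.

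- **Every patient who uses the steroid example is in breach.** A reader might infer this, but the PD-1 decision can precede enrolment. A patient who has since come off steroids breaches nothing.
- **Sites will handle these patients differently.** Appendix B requires a concomitant medication list before registration and has the coordinating team determine eligibility. Section 4.4 and Appendix E (3.7.1) route outside sites through central verification. A steroid user should be visible before treatment, although the central reviewer would still have no written rule to apply.
- **Anti-epileptic drugs show the same conflict.** Section 5.4.2 also prohibits "Anti-epileptic drugs for subjects with treated brain metastasis". Exclusion 6, however, admits nobody because of anti-epileptic use, and a patient with treated metastases who takes no such drug satisfies both provisions. That is an ordinary concomitant-drug restriction.
- **There is an uncontrolled hyperglycemia risk.** If Section 5.4.2 is followed, the steroid exposure does not occur. Glucose is also covered by the entry limits, exclusion 9, home monitoring and Table 5.

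**Conclusion.** The conflict is real and narrow. Two operative rules cannot both be followed for a clear-cell patient who enters on the steroid-based PD-1 waiver and still needs oral or IV systemic steroids at Cycle 1 Day 1.

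The conclusion rests on two readings. The first is that the example in criterion 4, worded in the present tense, describes a continuing need. The second is that neither the discretion clause nor criterion 10 displaces a specific prohibition.

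The size cannot be estimated. The documents do not give the number of such patients, and it may be small or zero. One patient would be 1/40 = 2.5% of planned enrolment, but that is the weight of a single subject and not a frequency. The primary endpoint definition, type I error and power are untouched. This is an inconsistency in wording that bears on patient care and protocol compliance, not a flaw in the statistical design.

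**What to change.** Reconcile criterion 4 of Section 3.1 with the steroid entry in Section 5.4.2, and carry the result into Section 3.2 and the eligibility checklist as needed, so that the entry rule and the on-study rule for systemic steroids agree. The reconciled text should make clear how a steroid requirement already present at entry is to be handled. Which rule stands is a clinical decision for the sponsor's clinicians, and this review takes no position on it.

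The cost is a wording amendment with matching checklist text. It needs no new procedure, data item or sample size change, and few if any patients would see their eligibility change.

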### 3.2 Exclusion criteria

1. Subjects with a history of deep vein thrombosis (DVT) or pulmonary embolism (PE) within 6 months of study treatment initiation.
2. Receipt of any type of small molecular kinase inhibitor (including investigational kinase inhibitors) within 2 weeks of enrollment or receipt of any anti-cancer therapy (including investigational therapy, monoclonal antibodies, cytokine therapy) within 3 weeks of enrollment.
3. Treatment with any investigational products within 3 weeks before the first dose of study drug.
4. Radiation therapy for bone metastases within 2 weeks, other external radiation therapy within 4 weeks of enrollment.
5. Received prior hemibody external radiotherapy.
6. Known brain metastases or cranial epidural disease unless adequately treated with radiotherapy, radiosurgery, or surgery and stable for at least 4 weeks prior to enrollment as documented by magnetic resonance imaging (MRI) or computed tomography (CT) imaging. Treated brain metastases are defined as having no ongoing requirement for steroids and no evidence of progression or hemorrhage after treatment for at least 4 weeks prior to enrollment as documented by MRI or CT imaging.
7. Imminent or established spinal cord compression based on clinical and/or imaging. In subjects with untreated imminent or established spinal cord compression, treatment with standard of care as clinically indicated should be completed at least 4 weeks before enrollment.
8. The subject has a history of any of the following within the last 6 months before administration of the first dose of the drug:
  - Ischemic myocardial event, including angina requiring therapy and artery revascularization procedures
  - Ischemic cerebrovascular event, including transient ischemic attack and artery revascularization procedures

- Requirement for inotropic support (excluding digoxin) or serious (uncontrolled) cardiac arrhythmia (including atrial flutter/fibrillation, ventricular fibrillation or ventricular tachycardia)
  - Placement of a pacemaker for control of rhythm
  - New York Heart Association (NYHA) Class III or IV heart failure
  - Significant active cardiovascular or pulmonary disease including:
    - Uncontrolled hypertension defined as sustained BP >160 mm Hg systolic or > 95 mm Hg diastolic despite optimal antihypertensive treatment.
    - Pulmonary hypertension
    - Uncontrolled asthma or O2 saturation < 90% by arterial blood gas analysis or pulse oximetry on room air
    - Significant valvular disease; severe regurgitation or stenosis by imaging independent of symptom control with medical intervention, or history of valve replacement
    - History of arrhythmia requiring an implantable cardiac defibrillator
    - Medically significant (symptomatic) bradycardia
9. Poorly controlled diabetes mellitus defined as glycosylated hemoglobin (HbA1c) > 7%; subjects with a history of transient glucose intolerance due to corticosteroid administration may be enrolled in this study if all other inclusion/exclusion criteria are met
10. Active gastrointestinal (GI) disorders including those associated with a high risk of perforation or fistula formation. Subjects with enteric stomata (such as ileostomy, colostomy) are also excluded:
- Tumors invading the GI-tract, active peptic ulcer disease, inflammatory bowel disease, diverticulitis, cholecystitis, symptomatic cholangitis or appendicitis, acute pancreatitis or acute obstruction of the pancreatic or biliary duct, or gastric outlet obstruction.
  - Abdominal fistula, gastrointestinal perforation, bowel obstruction, or intraabdominal abscess within 12 weeks before enrollment. **NOTE:** Complete healing of an intra-abdominal abscess must be confirmed before enrollment.
11. Clinically significant hematemesis or hemoptysis of > 0.5 teaspoon (2.5 ml) of red blood, or other history of significant bleeding (such as pulmonary hemorrhage) within 4 weeks of enrollment.
12. Other clinically significant disorders such as:
- Known active infection requiring systemic treatment, infection with human immunodeficiency virus (HIV) or acquired immunodeficiency syndrome (AIDS)-related illness, chronic hepatitis B or known or suspected active hepatitis C infection.
  - Serious non-healing wound or ulcer.
  - Malabsorption syndrome.
  - Symptomatic hypothyroidism.
  - Moderate to severe hepatic impairment (Child-Pugh B or C).
  - Requirement for hemodialysis or peritoneal dialysis.
  - History of solid organ transplantation.

13. Major surgery (such as GI surgery) within 6 weeks of enrollment. However, subjects who have had a nephrectomy may be enrolled 4 weeks after surgery, providing there are no wound-healing complications. Subjects with clinically relevant ongoing complications from prior surgery are not eligible. The following are not considered to be major procedures: Thoracentesis, paracentesis, port placement, laparoscopy, thoracoscopy, bronchoscopy, endoscopic ultrasonographic procedures, mediastinoscopy, skin biopsies, incisional biopsies, imaging-guided biopsy for diagnostic purposes, and routine dental procedures.
14. QTcF (Fridericia formula for the QT interval correction for the heart rate) > 480 msec within 4 weeks of enrollment. If the initial QTcF is found to be > 480 msec, two additional electrocardiograms (EKGs) separated by at least 3 minutes should be performed. If the average of these three consecutive results for QTcF is  $\leq$  480 msec, the subject meets eligibility in this regard. Subjects with history of congenital long QT syndrome, or torsades de pointes, are not allowed.
15. Pregnant or lactating females.
16. Inability to swallow tablets or capsules.
17. Previously identified allergy or hypersensitivity to components of the study treatment formulations.
18. Malignancies other than RCC within 5 years of first study treatment with the exception of those with negligible risk of metastases or death (carcinoma in situ of the cervix, basal or squamous cell skin cancer, localized prostate cancer, ductal carcinoma in situ of the breast, non-muscle invasive urothelial carcinoma).
19. Any serious medical or psychiatric illness that could, in the site investigator's opinion, potentially interfere with the completion of treatment according to this protocol.
20. Daily or chronic use of a proton pump inhibitor (PPI) and/or having taken a PPI within 7 days before receiving the first dose of study drug.

